### 12.3 Exploratory Objectives

- 12.3.1 To evaluate heterogeneity of tumor FFNP uptake.

The coefficient of variation (COV), defined as standard deviation of the standardized uptake value (SUV) and the mean value of the SUV will be assessed. Other descriptive measures such as skewness and kurtosis, which are measures of asymmetry and heaviness of the tails, relative to the normal distribution will be assessed. The analysis will be done separately for each reader.

- 12.3.2 To correlate tumor FFNP uptake with serum progesterone and estradiol levels.

A correlation analysis of serum progesterone and estradiol levels with tumor FFNP uptake measured with SUV values will be performed using Pearson's or Spearman's rank correlation. Scatter plots, correlation coefficients (rho), 95% confidence intervals, and p values will be reported. This analysis will be done separately for each reader.

- 12.3.3 To correlate tumor FFNP uptake with disease recurrence.

If there is sufficient follow-up data for disease recurrence, the Kaplan-Meier method will be used to analyze time to disease recurrence, defined as date of imaging day until disease recurrence.

Patients who do not experience disease recurrence will be censored at the date of last available follow-up. A Cox proportional hazards model will be used to evaluate the association of tumor FFNP uptake with time to disease recurrence. If there is insufficient follow-up data, descriptive statistics will be used to summarize the tumor FFNP uptake for those patients with disease recurrence.

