#### 3.3 Exploratory objectives:

- To evaluate heterogeneity of tumor FFNP uptake.
- To correlate tumor FFNP uptake with serum progesterone and estradiol levels.
- To correlate tumor FFNP uptake with disease recurrence.

Study duration: 36 months. Our estimated rate of accrual is 1 participant per month.

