## 12. STATISTICAL CONSIDERATIONS

### 12.1 Primary Objective

12.1.1 To compare FFNP uptake of biopsy-proven primary PR+ breast malignancies measured using PET/MRI with the reference standard of PR immunohistochemistry (IHC).

The primary objective is to compare FFNP  $SUV_{max}$  from PET/MRI with the PR immunohistochemistry semi-quantitative score obtained by using the Allred score (0-8) (1). The correlation of the two measures will be evaluated with Pearson's correlation coefficient. The null hypothesis is  $H_0: p_0=0.20$  and the alternative hypothesis is  $H_1: p_1=0.70$ .

A sample size of 21 patients achieves 80% power to detect this difference, using a two-sided hypothesis test with a Type I error of 5%, accounting for 1 dropout. Sample size calculations were done in PASS 14 (NCSS, LLC, Kaysville, Utah. <http://www.ncss.com>).

Other measures of FFNP uptake including  $SUV_{peak}$  (small fixed-size ROI centered on most metabolically active part of tumor),  $SUV_{mean}$  (average value), tumor-to-normal tissue uptake ratio, and total lesion uptake (functional tumor volume  $\times$   $SUV_{mean}$ ) will also be correlated with the PR immunohistochemistry semi-quantitative score obtained by using the Allred score.

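### Section 12.3.3: the recurrence fallback summarises FFNP uptake only in patients who recur, so that branch cannot relate uptake to recurrence

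*Combined protocol and SAP*

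**What the plan says.** Section 3.3 gives the third exploratory objective as "To correlate tumor FFNP uptake with disease recurrence". Section 12.3.3 plans two routes to it.

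- **Main route.** "If there is sufficient follow-up data for disease recurrence, the Kaplan-Meier method will be used to analyze time to disease recurrence", with time counted from imaging day. Then "A Cox proportional hazards model will be used to evaluate the association of tumor FFNP uptake with time to disease recurrence". Patients without recurrence stay in this analysis: "Patients who do not experience disease recurrence will be censored at the date of last available follow-up".
- **Fallback.** When follow-up data are insufficient, "descriptive statistics will be used to summarize the tumor FFNP uptake for those patients with disease recurrence".

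The documents do not define what counts as sufficient and give no minimum number of recurrences. No other section adds a summary of uptake in patients who do not recur. Under Sections 5.9 and 7.4, recurrence is read from medical records at the end of the study where follow-up is available, with a minimum of one year after surgery. Section 5.5.6 has uptake quantified for the known lesions on the research scans, so the values exist whatever the later outcome.

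**The concern.** An association between uptake and recurrence is a contrast: uptake in those who recur against uptake in those who do not. The fallback reports one side of it. Followed as written, it gives a mean or range for the few patients who recur with nothing to judge it by, or no result if none recur. In a trial of this size the fallback may well be the route taken. The final report would then list a result under this objective that does not bear on it, while the uptake values that would make it readable sit unused in the same database.

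**Working it through.** **Plan's own figure.** None is stated for recurrence. The only sample-size figure, 21 patients, is set for the primary correlation (0.20 against 0.70, 80% power, 5% type I error, one dropout; Section 12.1). Two-sided by Fisher z: ((1.960 + 0.842) / (atanh 0.70 - atanh 0.20))² + 3 = (2.802 / 0.6646)² + 3 = 20.8, so 21 evaluable plus 1 dropout = 22. Simulating the distribution of r gives 80.5% power at 20, and 20 + 1 = 21. The figure reproduces, but it says nothing about recurrence.

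**Step 1: what each branch can show.**
- Cox: each recurrence is compared with everyone still at risk, so patients who have not recurred contribute. The analysis is of the right type for the objective.
- Fallback: only patients who recur. The same summary is compatible with higher, equal or lower uptake in the others, so neither the direction nor the size of a relation can be read from it. This holds at any sample size and any recurrence rate.

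**Step 2: how many recurrences to expect.** The documents give no rate, so 1-5% per year is an assumption.
- Patients: 21 plus up to 5 PR-negative (Section 1, Number of Subjects). I take 26, reading the 5 as additional and assuming follow-up on everyone.
- Mean follow-up: 1.5 to 2 years assumed. As a check, entry at one per month, read at month 36 (Section 3.3), gives 23.0 months for 26 patients and 25.5 months for 21.
- Expected recurrences = patients × years × rate: 26 × 1.5 × 0.01 = 0.39, up to 26 × 2 × 0.05 = 2.6.
- Chance of none = exp(-expected): exp(-0.39) = 68%, down to exp(-2.6) = 7%.
- Using the month-by-month entry schedule instead, 1-5% per year gives 0.5 to 2.4 recurrences (26 patients) or 0.4 to 2.2 (21 patients). Even at 10% per year it gives 4.7 or 4.2.

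**Step 3: precision of the Cox branch.** The standard error of the log hazard ratio per SD of uptake is roughly 1/√d for d recurrences, so the 95% interval extends by a factor exp(1.96/√d) each way.

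| Recurrences | Factor each way |
|---|---|
| 1 | 7.1 |
| 2 | 4.0 |
| 3 | 3.1 |
| 5 | 2.4 |

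This is a large-sample approximation and is unreliable at one event. Recurrences needed for 80% power at two-sided 5% are (1.960 + 0.842)² / (ln HR)²: 17 for a hazard ratio of 2 per SD and 7 for 3 per SD. In simulation (1,500 runs per scenario; 2-10% per year; hazard ratio 1.5 to 3 per SD), Cox power was at most about 52%.

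**Step 4: what a two-group fallback would add.** It makes the contrast visible but stays descriptive. In the same simulations an exact Wilcoxon comparison of patients with and without recurrence had power between 1% and 42%.

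**The case against.** The strongest reply is that this is the last of three exploratory objectives. It has no hypothesis, error rate, power or event target, and the plan itself anticipates thin data. Imprecision is to be expected, and the imaging does not guide care. All of that stands and sets the severity. It excuses low power, but not a summary that omits one side of the comparison.

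A reader might infer three stronger things that the documents do not support.

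- *That neither branch can answer the objective.* The gap in the fallback is structural. The Cox branch is only imprecise, and that depends on an assumed recurrence rate. A very large effect with a high rate could still show.
- *That data from patients without recurrence are discarded altogether.* They are left out of the fallback only. The Cox branch includes them as censored.
- *That the switch ignores events.* The main condition refers to follow-up data for disease recurrence, which can be read to include observed recurrences. The fallback condition lacks those words, and the threshold is undefined in both, but the text does not settle the stricter reading.

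**Conclusion.** The point holds for the fallback branch. As written, it cannot address the objective it serves, and it is empty if there are no recurrences. That conclusion follows from the text and needs no assumed rate.

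The assumed rate bears only on how much this matters. At 1-5% per year, with 26 patients and 1.5 to 2 years of mean follow-up, about 0.4 to 2.6 recurrences are expected, with a 7% to 68% chance of none. Incomplete follow-up, or fewer than 5 PR-negative patients, would lower the count.

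A reader might also infer that the Cox model should be barred below some fixed number of recurrences. No threshold follows from the documents. A minimum of 10, for example, would be met with a Poisson probability of about 0.04% even at 2.6 expected, which in effect deletes the model. Stating the number of recurrences lets readers weigh any hazard ratio for themselves.

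The severity is minor. The objective is exploratory, and no primary or secondary result changes.

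**What to change.** In Section 12.3.3, replace the fallback sentence with: *tumor FFNP uptake will be summarised, with individual values plotted, for patients with and without recurrence, showing each patient's follow-up time from imaging day.* Imaging day is the time origin the section already uses, so no second clock is introduced.

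Add one sentence saying that this two-group description will be reported whether or not the Cox model is fitted, and that the number of recurrences will be given beside any hazard ratio. Less then hangs on where the line for sufficient follow-up is drawn.

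The cost is two sentences. Uptake, imaging date and recurrence status are already collected, and no visit, patient or test is added. The two-group display should be presented as description, not as a test of association.

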#### **12.4 Evaluation of Toxicity**

Subjects will be evaluable for toxicity from the time of injection of FFNP until 24 hours after injection. For this evaluation, the study coordinator will contact the subject within 1 to 3 days after FFNP administration.

### **13. PATHOLOGY REVIEW**

#### **13.1 Justification**

The primary objective is to measure FFNP uptake of biopsy-proven primary PR+ invasive breast malignancies using PET/MRI. The reference standard will be PR expression measured with immunohistochemistry.

The pathology of the biopsy-proven breast cancer will be evaluated per the current standard of care (histologic diagnosis, grade, ER status, PR status, HER2 status, Ki67 score). At UW Health, Ki67 score is routinely reported as a percentage of darkly stained nuclei across the entire tumor represented on the stained slide. At UW Health, PR status is routinely reported as positive or negative and includes a visual estimation of the percentage of cells staining positive as well as intensity of staining. This information will be obtained from the pathology report in the subjects' electronic medical record and will be used to calculate a semi-quantitative Allred score (1). If the information needed to calculate the Allred score is not included in the clinical pathology report, a pathologist on the research study team will review the existing PR IHC slides.

#### **13.2 Required Pathology Materials**

Pathology reports will be available through the electronic medical record. Existing pathology slides (PR IHC and H&E) from the breast biopsy used for initial diagnosis will be requested from the Department of Pathology for semi-quantitative Allred scoring by the research study pathologist if the information needed to calculate the Allred score is not included in the clinical pathology report.

For the research-based Oncotype DX score, a study pathologist will review the H&E slides from the surgical specimen and select a block for release to

the TRIP Laboratory. We anticipate needing 6 unstained sections per patient specimen for sufficient RNA isolation for the assay.

### 13.3 Routing

Requested pathology slides will be sent to the research study pathologists.

## 14. RECORDS TO BE KEPT

The PI will supervise the data collection and management. The following types of data and materials will be collected:

### 14.1 Images

Images from the research imaging examinations will be stored on the local picture archiving and communication system (PACS) (McKesson, San Francisco, CA). The local PACS system is password protected behind the UW Department of Radiology firewall.

### 14.2 Regulatory and Consent

A research chart will be created for each subject. The chart will include the signed consent form, a copy of the subject's experimental bill of rights, and a signed HIPAA form. Research charts will be kept in a locked file cabinet within a secure office. An enrollment log will be maintained. The enrollment log will confirm that informed consent was obtained on each subject. The patient has the right to decline to participate in the study and to request removal from the study at any time. Informed consent will be provided and signed prior to enrollment in the study. Patients may refuse to answer any questions asked during the duration of the study if they are too uncomfortable to answer. All of these potential risks will be described to the patient in the informed consent document.

### 14.3 Confidentiality

Information about study subjects will be kept confidential and managed according to the requirements of the Health Insurance Portability and Accountability Act of 1996 (HIPAA). Subjects will be assigned a unique study number upon enrollment that will be used to label their research data in lieu of directly identifiable information. All subject data collected during participation in the study will be kept in a locked file cabinet within a secure office or a password-protected database that uses departmental servers and will only be accessible to study team members. After the study is completed, all data will be de-identified for the purposes of research presentations/publications. The study breast MRI examinations will be archived on the standard clinical PACS system which is password protected behind the UW Health firewall. The study data and records will be maintained for up to 5 years after the conclusion of the study, at which point the PI will destroy the key to the coded identifiers, thus permanently anonymizing the data.

## **15. PATIENT CONSENT AND PEER JUDGMENT**

Current FDA, state, federal, and institutional regulations concerning informed consent will be followed.

## **16. DATA AND SAFETY MONITORING**

Safety monitoring of research protocols investigating novel PET tracers utilize a combination of tools. These are framed to provide adequate clinical trial oversight ensuring that the research team is complying with the conditions of IRB approval and FDA requirements. The tools enable frequent evaluations of study-related activities, identification of deviations or noncompliance with the conduct of the study or protocol, review of adverse events tracking and reporting, and review of drug production and accountability.

These tools include:

- Study visit checklists – Research Coordinators use study visit checklists, developed in conjunction with the PI, to ensure that all study required procedures and processes are met before, during and after the subject has been enrolled. Items listed on these checklists include informed consent obtained, consent questions answered (and by whom), vitals recorded, medications reviewed, MRI safety form, etc. These checklists are completed and reviewed by the study coordinator requiring signature approval for each study subject to ensure tight adherence to the protocol.
- Safety monitoring – The safety monitoring of subjects enrolled in the research includes both internal and external safety checks governing the administration of FFNP. Internal monitoring is performed by co-investigators and external monitoring by a team of four physicians, scientists, and staff with the appropriate broad clinical and technical expertise. The internal monitoring plan includes a brief review of each subject visit after it occurs. In this regard, the study team will discuss data quality, FFNP production and administration, and subject compliance and tolerance of research procedures.

The external monitoring plan will be coordinated by the Department of Radiology Medical Imaging Research Support (MIRS) administrative team. MIRS is a working group that provides investigators with the support needed to conduct clinical research that uses imaging as an outcome measure. Members include a core administrative group (physicians, scientists, imaging modality managers, regulatory and administrative support) and ad hoc members recruited when their expertise is required for the review/monitoring of a research project. MIRS administrative team in addition to a 4-person committee of physicians/scientists will meet annually with representatives from the research team, to discuss research progress, AE/SAE reports, as well as other data reports compiled by the study team. If an AE/SAE occurs, an ad hoc committee meeting will be organized to discuss whether the event is considered serious, whether it can be attributed to research procedures, whether it constitutes non-compliance on the part of the study team, and the plan for resolution and a future remediation plan.

As part of this plan, the monitor(s) will verify that:

- The rights and well-being of human subjects are protected
- Reported study data are accurate, complete, and verifiable from source documents
- The conduct of the study is in compliance with the currently approved protocol, GCPs, applicable regulatory requirements, and guidelines for clinical research studies at the University of Wisconsin-Madison and its affiliates

## 16.1 Risks

### 16.1.1 MRI

The risk from the MRI component of the exam is minimal and is primarily related to claustrophobia and discomfort with positioning. Only staff skilled in the placement of IVs will place IVs for the study breast PET/MRI. Injection of gadolinium contrast has common mild side effects, including nausea, headache, and hives. More serious reactions, while rare, can occur, including allergic reactions. Any significant allergic reaction or contrast extravasation will be monitored and treated appropriately by clinical staff.

All hardware used to obtain MR images is FDA approved and will be used in accordance with the conditions approved by FDA. The investigational software being used in image acquisition is designed to stay within the current guidelines for MRI safety, established by the FDA. In addition, the investigational software does not meet the definition of a Significant Risk Device as outlined by the FDA under 21 CFR 812.3 as being:

- Intended as an implant and presents a potential for serious risk to the health, safety, or welfare of a subject;
- Purported or represented to be for use supporting or sustaining human life and presents a potential for serious risk to the health, safety or welfare of a subject;
- For a use of substantial importance in diagnosing, curing, mitigating, or treating disease, or otherwise preventing impairment of human health and presents a potential for serious risk to the health, safety or welfare of a subject; or
- Otherwise presents a potential for serious risk to the health, safety, or welfare of a subject.

### 16.1.2 PET

There has been one “first-in-human” study involving 20 patients using FFNP PET/CT (11). There were no adverse events, changes in vital signs, laboratory values or electrocardiograms, or clinically detectable pharmacologic effects. Similarly, there were no adverse events or clinically detectable pharmacological effects associated with FFNP administration in

a subsequent phase 2 study involving 43 patients each receiving 2 FFNP PET/CT scans (12).

Risks associated with PET imaging result primarily from the radiation dose from the radiopharmaceutical. For this research study, approximately 7 mCi of FFNP will be administered intravenously which is also the standard dose used for other clinical trials using FFNP (11,12). The radiation effective dose equivalent to the whole body from intravenously injected FFNP is estimated to be 0.02 mSv/MBq (11). Thus for an administered dose of 7 mCi (259 MBq), the whole-body effective dose equivalent is approximately 5 mSv. The dose-limiting organ is the gall bladder, with an average absorbed dose of 0.113 mGy/MBq. The average absorbed dose to the breasts is 0.010 mGy/MBq and the whole-body dose is 0.015 mGy/MBq. Thus for an administered dose of 7 mCi (259 MBq), the whole-body absorbed dose is approximately 3.885 mGy. For context, the average person in the United States receives an estimated effective dose of about 3 mSv per year from naturally occurring radioactive materials, such as radon and radiation from outer space. The current guidance from radiation protection organizations, including American Association of Physicists in Medicine, Health Physics Society, International Organization for Medical Physics, and United Nations Scientific Committee on the Effects of Atomic Radiation (UNSCEAR) states that estimates of risk below levels of about 100 mSv are not statistically different from zero. The organ and total body doses associated with FFNP-PET imaging are comparable to or lower than those associated with other widely used clinical nuclear medicine procedures and are well below the maximum suggested individual study and annual total body dose of 30 and 50 mGy, respectively, suggested for investigational radiopharmaceuticals by the FDA.

16.1.3 CT (performed only in rare instances when the subject is unable to be imaged using the simultaneous PET/MRI scanner).

Risks associated with CT include exposure to 1.5 mSv of radiation from the low-dose chest CT scan required for attenuation correction calculations. Thus, the total whole body effective dose equivalent for breast PET/CT is approximately 6.5 mSv. This corresponds to approximately 2 years of natural background radiation and remains well below the annual occupational dose limit for radiation workers.

#### 16.1.4 Scanner/Tracer Production Issues

There is a possibility of tracer production issues and scanner malfunction issues. These two issues are rare but not unanticipated. When possible, subjects will simply be rescheduled to a day/time that fits their schedules. If PET tracer has been administered prior to the discovery of a scanner issue, subjects will be paid and withdrawn from this research. The research

team will call the subject within 3 days to inquire about adverse events related to the tracer.

#### 16.1.5 Unexpected findings

All patients in this study will receive the clinical “gold standard”, diagnostic breast MRI and PR measurement via IHC, as part of their clinical care as a requirement for enrollment in the study. Thus, the breast specific PET/MRI research study is not expected to yield any additional information beyond that which was described on the diagnostic exam. Additionally, breast specific PET is not routinely used in clinical practice for local staging and extent of disease and this information will not be used to guide clinical care. For these reasons, incidental findings may not be identifiable (poor quality images) or may not be identified until long after the research exam is performed. Thus, PET images will not be reviewed by a radiologist as a diagnostic exam.

